## 6.6 Additional treatment guidance

### 6.6.1 Treatment compliance

The investigator must promote compliance by instructing the participant to take the study treatment exactly as prescribed and by stating that compliance is necessary for the participant's safety and the validity of the study. The participant must also be instructed to contact the investigator if he/she is unable for any reason to take the study treatment as prescribed.

Compliance will be assessed by the investigator and/or study personnel at each visit using pill counts (if applicable) and information provided by the participant. This information should be captured in the source document at each visit. All study treatment dispensed and returned must be recorded in the Drug Accountability Log.

Where applicable, remote treatment administration compliance will be assessed by the OHP and information will be provided to the Investigator and/or study personnel.

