## 6 Statistical methods for Efficacy/Pharmacodynamic (PD) parameters

All participants within the efficacy/PD analysis set will be included in the efficacy/PD data analysis.

Data will be excluded from the efficacy/PD analyses in the following cases:

- For participants with protocol deviations affecting the efficacy/PD analyses, the data will be excluded as described in [Table 4-1](#) above.
- For participants that discontinued treatment early, the following *programming rule* will be applied: *Any efficacy assessments that occurred on or after the treatment discontinuation study day, will be excluded from all efficacy/PD data analyses. An exception to this is the Day 85 visit or EOS visit imaging data (MRI and MRE assessments), that will be excluded only if they occurred prior to study day 56 (i.e., imaging assessments that occurred on or after study day 56, will not be excluded from the imaging analyses).*
- Participants with <80% treatment compliance

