### Treatment compliance calculation

For each subject, the treatment compliance (%) will be calculated using the following formula:

$$100 * \left( \frac{\text{Number of capsules expected to be taken up to the last treatment day} - \text{Number of capsules missed during the treatment period}}{\text{Number of capsules expected to be taken up to the last treatment day}} \right)$$

where,

*Number of capsules expected to be taken up to the last treatment day =*  
last treatment day \* CCI , if treated with LYS006

OR

last treatment day \* CCI , if treated with LJN452

*Number of capsules missed during the treatment period =*  
Sum (Number of capsules expected to be taken in the dosing modification period x - Number of capsules actually taken in the dosing modification period x)

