#### Notes:

- The treatment compliance will be calculated separately for each treatment (LYS006 and LJN452).
- The last treatment day is defined as the last available start or end treatment day, as reflected in the dosing dataset.

- A dose modification period is a period with either a dose change or a dose interruption. These periods will be identified in the dosing dataset under records with TYPE OF CHANGE='DOSE CHANGED' and TYPE OF CHANGE='DOSE INTERRUPTED', respectively.
- For the dose modification periods:
  - Only the dosing records with non-missing dose administered, non-missing start date and non-missing end date will be considered in the calculations.
  - Dose administered = Number of capsules administered
  - The number of capsules expected to be taken in a dosing modification period =  
(period end day – period start day +1) \* CCI , if treated with LYS006  
OR  
(period end day – period start day +1) \* CCI , if treated with LJN452
  - The number of capsules actually taken in a dosing modification period =  
(period end day – period start day +1) \* dose administered
  - The frequency of dose administered will not be considered in the calculations, only the dose administered itself.

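### The SAP's 80% compliance rule scores an incomplete dose-change or interruption record as full adherence, and does not count capsules skipped without such a record

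*SAP*

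**What the plan says.** SAP section 6 lists the cases in which data leave the efficacy/PD analyses. One of them is "Participants with <80% treatment compliance".

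The score is computed separately for LYS006 and LJN452, as 100 × (expected − missed) / expected. Missed capsules are the sum, over modification periods, of "Number of capsules expected to be taken in the dosing modification period x - Number of capsules actually taken" in that period. The notes to the calculation define the term: "A dose modification period is a period with either a dose change or a dose interruption". The periods are found through the codes DOSE CHANGED and DOSE INTERRUPTED. The notes then add: "Only the dosing records with non-missing dose administered, non-missing start date and non-missing end date will be considered in the calculations". The denominator is the last treatment day times a daily capsule number (redacted), and "The last treatment day is defined as the last available start or end treatment day, as reflected in the dosing dataset". The visible SAP text does not mention returned capsules or the accountability log.

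Protocol 6.6.1 describes compliance differently: "Compliance will be assessed by the investigator and/or study personnel at each visit using pill counts (if applicable) and information provided by the participant". The result goes into the source document, and supplies given out and brought back go into the Drug Accountability Log. Under the footnotes to Protocol Table 8-1, oral drug is self-administered from Day 2 to Day 84, apart from marked visit days.

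**The concern.** Every day outside a complete modification record counts as fully dosed. Two things follow.

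- A DOSE CHANGED or DOSE INTERRUPTED record with a blank dose, start date or end date drops out of the sum. Missing information about an interruption is thus scored as if no capsule was missed.
- Capsules skipped at home without such a record do not enter the sum, even where a pill count would show them.

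Two participants with the same drug intake can then fall on opposite sides of the 80% limit because one field was completed for one of them and not for the other. The analyses concerned include ELF, ALT and % liver fat, which Protocol 4.1.3 names as the evidence of efficacy. With about 20 evaluable participants per arm (Protocol section 5), one wrong classification is 1/20 = 5% of an arm.

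**Working it through.** The plan gives no compliance figure to reproduce, so the check applies the SAP formula to constructed cases.

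**Inputs**
- Cut-off: below 80% (SAP section 6).
- Treatment length L: 85 days, since SAP 1.4 runs treatment from Day 1 to Day 85; 84 is the alternative.
- Daily capsules c: redacted. For m whole days missed it cancels: 100 × (Lc − mc)/(Lc) = 100 × (L − m)/L.

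**Where the limit falls.** With L = 85, 17 missed days give 68/85 = 80.0% (kept) and 18 give 67/85 = 78.8% (excluded). With L = 84, 17 missed days give 67/84 = 79.8% (excluded).

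**Score by state of the record (L = 85)**

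| Days missed | True compliance | SAP score, complete interruption record | SAP score, end date or dose blank | SAP score, no record |
|---|---|---|---|---|
| 18 | 67/85 = 78.8% | 78.8% | 100% | 100% |
| 25 | 60/85 = 70.6% | 70.6% | 100% | 100% |
| 30 | 55/85 = 64.7% | 64.7% | 100% | 100% |

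The formula is right when the record is complete. In the last two columns no missed capsules are counted, so the score is (85 − 0)/85 = 100%. These columns assume that other dosing records run to Day 85 and that there is no other modification period. A participant with further, complete periods would score less than 100% but still too high.

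**Closing an open end date**
- *A later record exists.* The interruption starts on Day 36, its end date is blank, and the next record runs from Day 61 to Day 85. Closing at Day 60 gives 60 − 36 + 1 = 25 missed days and (85 − 25)/85 = 70.6%.
- *No later record exists.* The interruption starts on Day 61 with no end date. The SAP's last treatment day is then itself Day 61. As written, the SAP scores 61/61 = 100%. Closing the record at that same day counts one missed day, 60/61 = 98.4%, so this closure does not repair the score. If a date held outside the dosing dataset puts the end of treatment at Day 85, there are 85 − 61 + 1 = 25 missed days and the score is 60/85 = 70.6%.

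**The case against.** The case against is substantial.

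- **Cleaning.** Protocol 11.2 provides for queries on missing values, with lock only after the database is judged complete and accurate. The SAP rule then applies only to records still incomplete at lock.
- **A route for missed doses.** Protocol Table 10-1 sends unintentional treatment errors to the dosing CRF, with or without an adverse event. Some skipped doses may therefore become complete records, which the formula counts correctly.
- **TRT03.** SAP Table 4-1 removes efficacy/PD data from the deviation day onwards when the modification guidelines were not followed and an interruption exceeded 2 days. A 25-day interruption would ordinarily raise it.
- **Permanent stops.** SAP section 6 already drops efficacy data from the discontinuation day, apart from imaging on or after study day 56.
- **Scope.** Only secondary efficacy/PD analyses of a non-confirmatory study are affected.

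These points limit how often the flaw matters. They do not remove it. The SAP restriction itself provides for incomplete records at analysis. Nothing visible says that a pill-count shortfall becomes one of the two coded record types. TRT03 needs a logged deviation, leaves earlier data in, and would not catch scattered skipped capsules.

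Three stronger readings are tempting, and the documents do not support them.

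- A reader might infer that the SAP contradicts the protocol by not using pill counts. Protocol 6.6.1 makes them conditional and keeps them in source documents and the accountability log. It does not make them the analysis variable.
- A reader might infer that the treatment effect is diluted. Nothing shows how many participants are affected, no dilution can be quantified, and keeping low compliers is arguably less selective than removing them after randomization.
- A reader might infer that the score always errs upwards. If a permitted reduction is made with fewer capsules (an assumption, because capsule numbers are redacted), it counts as missed. Half the capsules from Day 15 to Day 85 is 71 × 0.5 = 35.5 days' worth, so the score is 49.5/85 = 58.2% and the participant is excluded.

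**Conclusion.** The concern holds in a limited form. As written, the SAP gives a wrong compliance score whenever a dose-change or interruption with missed capsules is still incompletely recorded at lock. The score can reach 100% where the true value is 70.6% (25 of 85 days), and the participant then escapes the exclusion. Days skipped with no modification record have the same effect.

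The size in any one participant follows from the formula and does not depend on the redacted capsule numbers for whole-day omissions. It does rest on 84 or 85 dosing days and, for the 25-day example, on dosing records through Day 85. How many participants would be affected cannot be told from the documents, because the CRF completion rules and dataset specifications are not shown. The primary safety analysis is untouched. This should be corrected before database lock, mainly because the core of the correction is cheap.

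**What to change.** In SAP section 6, under the compliance calculation:

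1. For a DOSE INTERRUPTED record with no dose, set capsules taken to 0.
2. Close a missing end date at the day before the next dosing record. If there is none, close it at the end-of-treatment date recorded outside the dosing dataset, and use that same date as the last treatment day in the denominator. The documents do not name such a field for all participants. Protocol 9.1.1 has early discontinuation of treatment registered in the IRT, which is one possible source.
3. State how a missing start date, or a DOSE CHANGED record with no dose, is resolved, and list any such records still open at lock.
4. Where accountability data are available, reconcile the dosing dataset with capsules dispensed minus returned before lock.

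Items 1 to 3 need SAP wording and a little programming. Item 4 costs more, because the counts are not shown to be in the clinical database and unreturned capsules would need a rule. A few more participants may be excluded from the efficacy/PD analyses as a result.

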## 6.1 Primary efficacy objectives

There are no primary efficacy objectives for this study.

The primary objective of this study is related to the safety and tolerability of single or combination therapy during 12 weeks of treatment and is described in [Section 8](#).

## 6.2 Secondary efficacy objectives

The secondary efficacy objectives are:

1. To determine the effect of single or combination therapy on circulating markers of ongoing liver fibrosis
2. To determine the effect of single or combination therapy on intrahepatic lipid content
3. To determine the effect of single or combination therapy on cardiometabolic risk parameters
4. To determine the effect of single or combination therapy on circulating markers of liver and/or systemic inflammation.

### **6.2.1 Variables**

The secondary efficacy variables/endpoints related to the secondary efficacy objectives are:

1. Markers of liver fibrosis:
  - Enhanced Liver Fibrosis Test (ELF TestTM):
    - Hyaluronic acid (HA)
    - Tissue inhibitor of metalloproteinases (TIMP-1)
    - Amino-terminal pro-peptide of procollagen type III (PIIINP)
2. Magnetic Resonance Imaging (MRI):
  - Percent (%) liver fat as measured by Magnetic Resonance Imaging-Proton Density Fat Fraction (MRI-PDFF)
3. Cardiometabolic risk parameters:
  - Body weight
  - Waist circumference
  - Hip circumference
  - Waist to hip ratio
  - Homeostasis Model Assessment of Insulin Resistance (HOMA-IR)
  - Hemoglobin A1c (HbA1c)
  - Fasting glucose
  - Fasting insulin
  - Fasting lipid profile:
    - Total cholesterol
    - HDL-cholesterol
    - LDL-cholesterol
    - Triglycerides
    - Lipoprotein A
4. Liver function tests and liver and/or systemic inflammation markers:
  - Alanine aminotransferase (ALT)
  - High-sensitivity C-reactive Protein (hsCRP)

#### **Baseline definition:**

Baseline for ALT is defined as the mean of the last 2 non-missing measurements taken prior to the first dose of study drug administered at the Day 1 visit.

For all other secondary efficacy endpoints, baseline is defined as the last non-missing measurement prior to the first dose of study drug administered at the Day 1 visit.

All assessments (scheduled and unscheduled) will be considered into the derivation of the baseline.

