**Table 4-1 Biomarker inclusion criteria compared to normal range**

[figure not shown]
	ALT	Liver fat content (MRI-PDFF)	ELF Test
Normal value	29-33 IU/L (males) 19-25 IU/L (females)	< 5%	< 7.7
NEXSCOT inclusion criteria	≥ 43 IU/L and ≤ 5x ULN (males) ≥ 28 IU/L and ≤ 5x ULN (females)	≥ 8%	8.5-10.5
Reference	Kwo et al 2017	Petäjä and Yki-Järvinen 2016	Lichtinghagen et al 2013 , Vilar-Gomez and Chalasani 2018

In this study, ELF Test measurement will be conducted at screening (see [Section 5.1](#) Inclusion criteria), and participants with an ELF Test result within the range of 8.5-10.5 will be

eligible for participation in the study. The goal of using these ELF Test inclusion criteria is to enrich the study population for those subjects with a high likelihood of an ongoing fibrotic process in the liver (disease stage F1-F3) but do not yet have severe fibrosis or cirrhosis (stage F4). This ELF Test inclusion range is based on a weight-of-evidence analysis of the following reports:

- In their review of the current state-of-the-art of soluble liver fibrosis biomarkers, ([Vilar-Gomez and Chalasani 2018](#)) noted that the area under the receiver operating characteristic curve (AUROC) for ELF Test using 8.5-10.18 cut-off values to detect liver fibrosis ( $F \geq 2$ ) was 0.82 in a meta-analysis of adult and pediatric patients (n=1329) with chronic liver disease, including NAFLD.
- ([Lichtinghagen et al 2013](#)) proposed the following ELF Test cut-off values based on the results of this test in healthy volunteers (n=400) and the relationship of this test with liver biopsy staged fibrosis in patients with hepatitis C (n=39):
  - $\leq 7.7$  excluded fibrosis with high sensitivity
  - $\geq 9.8$  had high specificity for identification of fibrosis
  - $\geq 11.3$  discriminated cirrhosis
- ([The National Institute for Health and Care Excellence 2016](#)) proposed that NAFLD patients should have ELF Test as a measure of advanced liver fibrosis and proposed that a value of  $\geq 10.51$  was consistent with advanced liver fibrosis.
- ([Gungoren et al 2018](#)) showed that using an ELF Test cut-off of  $\geq 8.84$  was associated with a liver fibrosis score of  $F \geq 2$  at an AUROC of 0.89 in 46 patients with auto-immune hepatitis who have liver biopsy.

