**Table 4-2 Examples of placebo effect in published studies in NASH and NASH-like patient populations**

Investigational drug	Obeticholic acid (n=23)	Obeticholic acid (n=142)	NGM282 (n=27)	MGL3196 (n=42)	BMS986036 (n=26)
Duration (weeks)	6	12	12	12	16
%Δ ALT from baseline	35.5	-13.4	-2.2	-	-4.5
Relative %Δ liver fat from baseline	-	-	-3.0	-9.6	-
Δ ELF Test from baseline	0.3	-	0	0.1	-
Reference	Mudaliar et al 2013	Neuschwander-Tetri et al 2015	Harrison et al 2018a	Harrison et al 2018b, Abstract GS-009	Sanyal et al 2017

Commercially Confidential Information

Conversely, a review of multiple, recent studies in patients with NASH or a NASH-like (biomarker) phenotype shows that high efficacy, active treatment is associated with relative percent decreases in % liver fat (MRI-PDFF) and ALT of  $\geq 30\%$  ([Sanyal et al 2017](#); [Harrison et al 2018a](#); [Harrison et al 2018b](#)). Similarly, a decrease in ELF Test by  $\geq 0.3$  units or 3% can be considered evidence of a substantive, beneficial reversal in the ongoing liver fibrotic process ([Harrison et al 2018a](#)).

Commercially Confidential Information

Commercially Confidential Information

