#### 6.2.3.1 Dietary restrictions

On Day 1 and Day 85, all participants must fast (i.e., no food or liquid except water) for at least 8 hours prior to administration of study treatment. Fasting is a requirement for certain samples (e.g., biomarkers) that are collected at these visits.

It is recommended that participants fast for at least 4 hours prior to any MRI or Fibroscan assessment. Please refer to the SOM for more details.

During the entire treatment period, it is recommended that study treatment should be administered with a light meal unless stated otherwise in the respective cohort-specific [Section 17](#).

Participants can drink water *ad libitum* however, to ensure adequate hydration for urine collection (if applicable), participants should be encouraged to have a fluid intake of at least 240 mL every 4 hours during waking hours in addition to fluid taken with meals and medication.

Alcohol consumption is to be strongly discouraged, and should not exceed 20 g/day in females and 30 g/day in males. Alcohol should be avoided for 8 hours prior to and after intake of study medication.

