**Table 8-1 Assessment Schedule**

Commercially Confidential Information

Epoch	Screening		Treatment												Post-Treatment Follow-Up 1 	Post-Treatment Follow-Up 2 				
	Visit Name	Screening	Baseline	Treatment												EOS1	EOS2			
Days	-60 to -28	-27 to -1	1 	8 	15 	22 	29 				43 	57 				71 	85 	113	141	
Weeks	-9 to -4	-4 to -1	1	2	3	4	5				7	9				11	13	17	21	
Time (post-dose)	-	-	-	-	-	-	0h 	1h	2h	3h	4h	-	0h 	1h	2h	3h	4h	-	-	
Demography	X																			
Hepatitis and HIV Screen 	S																			
COVID-19 Test 8a		S																		
Pregnancy and assessments of fertility 	X	X	X				X					X				X	X	X		
Physical examination 	S	S	S	S	S							S				S	S	S		
Vital signs and body measurements 	X	X	X	X	X							X	X			X	X	X		
ECG evaluation	X	X	X	X												X	X	X		
Hematology	X	X	X	X	X							X	X			X	X	X		
Blood chemistry	X	X	X	X	X							X	X			X	X	X		
Urinalysis	X	X	X	X	X							X	X			X	X	X		
Coagulation panel 	X	X	X	X	X							X	X			X	X	X		
Fasting glucose, insulin, and lipids 			X													X				
PK blood collection 			X	X	X	X	X	X	X	X	X	X	X	X	X	X 	X 			
Conditional biomarker RNA 		X	X									X				X	X	X		
Central lab biomarkers 	X 	X	X									X				X	X	X		

Commercially Confidential Information

Epoch	Screening		Treatment												Post-Treatment Follow-Up 1 	Post-Treatment Follow-Up 2 				
	Visit Name	Screening	Baseline	Treatment																
Days	-60 to -28	-27 to -1	1 	8 	15 	22 	29 				43 	57 				71 	85 	113	141	
Weeks	-9 to -4	-4 to -1	1	2	3	4	5				7	9				11	13	17	21	
Time (post-dose)	-	-	-	-	-	-	0h 	1h	2h	3h	4h	-	0h 	1h	2h	3h	4h	-	-	

Commercially Confidential Information

Dose administration 			X	X 	X 	X 	X					X 	X				X 	X 	
Fibroscan 24,25,NR			X														X	X 	
MRI/MRE 27,NR			X														X	X 	
VAS (Visual Analog Scale) 			X														X		
Telephone follow-up				X	X											X			

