Concomitant therapies 	X																		
Adverse events	As required																		
Serious adverse events	As required																		
Comments	As required																		
Study completion information																	X	X	

X Assessment to be recorded in the clinical database

S Assessment to be recorded in the source documentation only

NR Non-remote, i.e. this assessment may not be performed remotely (i.e., must be performed at the originally qualified facilities).

 For treatments with an extended half-life, EOS1 will be required as a standard, non-EOS post-treatment follow up visit, and EOS2 will serve as the EOS visit. For all other treatments, EOS1 will serve as the EOS visit.

 If a participant discontinues study treatment early, the participant should be scheduled for a subsequent visit at which time all assessments at the EOS1 visit should be performed. For treatments with an extended half-life, if a participant discontinues early after EOS1, then the participant should be scheduled for a subsequent visit at which time all assessments at the EOS2 visit should be performed.

 Assessments to be performed pre-dose.

 All participants must fast for at least 8 hours prior to administration of study treatment.

 Visit will be conducted via telephone only. Participants are not required to present to the study site for assessments.

 Informed consent must be provided by all participants before any screening procedures are performed. The DNA assessment is optional and requires a separate informed consent to be signed.

Commercially Confidential Information

 Standard laboratory assays to be used for screening.

8a COVID-19 test highly recommended to be completed within 1 week prior to first dosing, as defined in Exclusion Criterion #29.

 Serum pregnancy tests will be performed at Screening and EOS; urine tests may be used at other time points.

 A complete physical examination is required at Screening, Day 1, Day 85, and at the study completion visit. A focused physical examination can be performed at all other visits where a physical examination is required. Please see protocol [Section 8.4](#) for more details.

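### ELF and hsCRP baselines use one pre-dose value although at least two are scheduled and ALT is already averaged: a modest, avoidable loss of precision

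*SAP*

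**What the plan says.** **Baseline rule.** SAP 6.2.1 says for ALT: "Baseline for ALT is defined as the mean of the last 2 non-missing measurements taken prior to the first dose of study drug". For ELF, hsCRP and the rest it says: "For all other secondary efficacy endpoints, baseline is defined as the last non-missing measurement prior to the first dose of study drug". Scheduled and unscheduled assessments both count.

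**Samples available.** In Protocol Table 8-1 the row "Central lab biomarkers" is marked at Screening, at Baseline (Day -27 to -1) and on Day 1. Footnote 17 says the row may include CRP and ELF, and part of that footnote is redacted. Footnote 18 limits the Screening sample to ELF. Day 1 carries the note "Assessments to be performed pre-dose", so the last pre-dose value will normally be the Day 1 value. That is inferred from the schedule; the SAP does not name Day 1 as the baseline visit. ELF therefore has three scheduled pre-dose values and hsCRP two.

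The table came through imperfectly in the text available, but other sections agree with this reading. Protocol 4.1.2 states: "In this study, ELF Test measurement will be conducted at screening". Protocol 5.1 lets ELF eligibility be met at screening or baseline. Protocol 6.2.3.1 says of Day 1 and Day 85: "Fasting is a requirement for certain samples (e.g., biomarkers) that are collected at these visits".

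**Use.** The Protocol summary gives an MMRM on the log ratio to baseline, with log baseline and its interaction with visit as covariates. SAP 6.2.2 also summarises unadjusted change and percentage change.

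**The concern.** The measurement noise of a single sample passes into every change from baseline and every ratio to baseline. For ALT the SAP reduces that noise by averaging. For ELF and hsCRP it does not, although the Baseline and Day 1 visits that normally supply the ALT average also supply these markers. No visible text explains the difference.

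ELF is one of three main efficacy markers. Protocol 4.1.3 treats "a decrease in ELF Test by" at least 0.3 units or 3% as meaningful, and about 20 evaluable participants per arm are expected. Protocol section 5 allows an arm to grow to about 50 if biomarker variability is higher than anticipated. Using samples already drawn costs less than recruiting. What is at stake is the width of the intervals around the ELF and hsCRP effects.

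**Working it through.** The visible text gives no SD, correlation or precision figure for ELF or hsCRP, so there is no plan figure to reproduce. All correlations and SDs below are assumptions. Variances are taken as equal and scaled to 1.

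**1. General formulas.** Let c be the correlation between the Baseline visit and Day 1, a between Day 1 and follow-up, and b between the Baseline visit and follow-up.

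- Unadjusted change, one value: 2(1 - a). Mean of two: 1 + (1 + c)/2 - (a + b).
- Baseline-adjusted residual, one value: 1 - a². Mean of two: 1 - [(a + b)/2]² / [(1 + c)/2].

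**2. Equal correlation (a = b = c = r).** The unadjusted change variance is 1.5(1 - r) against 2(1 - r), a ratio of 0.75. The adjusted variance is 1 - 2r²/(1 + r) against 1 - r²:

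| r | One value | Mean of two | Variance ratio | SE ratio | Equivalent n per arm (20/ratio) |
|---|---|---|---|---|---|
| 0.6 | 0.640 | 0.550 | 0.859 | 0.927 | 23.3 |
| 0.7 | 0.510 | 0.424 | 0.830 | 0.911 | 24.1 |
| 0.8 | 0.360 | 0.289 | 0.802 | 0.896 | 24.9 |
| 0.9 | 0.190 | 0.147 | 0.776 | 0.881 | 25.8 |

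The adjusted gain is thus 14% to 22% of variance, or 7% to 12% of SE. As an illustration, take an ELF SD of 0.8 (assumed), a between-arm difference of 0.3, 20 per arm and two-sided alpha 0.20, which matches the planned 80% intervals. Power rises from 65% to 71% at r = 0.7 and from 76% to 82% at r = 0.8.

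**3. Unequal correlation.**

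- c = 0.85, a = 0.80, b = 0.75. Unadjusted: (1 + 0.925 - 1.55)/0.40 = 0.375/0.40 = 0.94. Adjusted: (1 - 0.775²/0.925)/0.36 = 0.351/0.36 = 0.97. A small gain remains.
- c = 0.80, a = 0.80, b = 0.70. Unadjusted: (1 + 0.90 - 1.50)/0.40 = 1.00. Adjusted: (1 - 0.75²/0.90)/0.36 = 0.375/0.36 = 1.04. There is no gain, and the adjusted model loses slightly.

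In the adjusted model averaging helps only if (a + b)² > 2(1 + c)a². With c = a = 0.8, the right side is 3.6 × 0.64 = 2.304, whose root is 1.518, so b must exceed about 0.72. With c = a = 0.9, the right side is 3.8 × 0.81 = 3.078, whose root is 1.754, so b must exceed about 0.85.

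**4. Selection on ELF.** Null changes were simulated for participants with a screening or baseline ELF of 8.5 to 10.5. Population means were 8.8 to 9.6, SDs 0.8 and 1.0, and correlations 0.7 and 0.9, all assumed. The one permitted repeat test was not modelled. Mean null change was about zero from the Day 1 value, -0.03 to +0.005 units from the mean of two, and -0.04 to +0.01 from the mean of all three. Against the 0.3-unit effect, the largest two-value shift is about 0.03/0.3 = 10%. hsCRP is not an eligibility criterion, so this does not apply to it.

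**The case against.** The last pre-dose value is a valid and unambiguous baseline, and these are secondary endpoints in a non-confirmatory study. The ALT exception also has a plausible source: the protocol already averages two ALT results for eligibility (5.1) and uses the mean of the last two assessments for liver safety (16.1). No such rule exists for ELF or hsCRP. All of this stands. It makes the choice understandable, but it gives no reason against averaging the other two markers.

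The gain rests on correlations nobody has stated, and the Baseline visit can be up to 27 days before dosing. This also stands: steps 2 and 3 run from a clear gain to a slight loss. The loss case is demanding, because it needs the older sample to track follow-up noticeably worse than Day 1 does.

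Day 1 has real advantages. It is not named as an ELF selection value, which matters when within-arm change is read without a placebo arm. It is also fasted, like Day 85, while the Baseline visit has no stated fast. The simulated selection shift is small. The effect of fasting cannot be sized from the documents and is a fair reason to keep a sensitivity analysis.

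A reader might infer that the one-value rule creates spurious ELF responders. The only responder tabulation in the visible text is for liver fat, whose baseline this point leaves alone. A reader might also infer that the three-part analysis of ELF, ALT and liver fat is compromised by unlike baselines. Differing baseline precision does not invalidate a multivariate ANCOVA, and liver fat would keep a one-value baseline in any case.

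**Conclusion.** The point holds as a modest loss of precision for ELF and hsCRP. It does not support a reading of bias or error. In the planned baseline-adjusted model, averaging two values saves about 14% to 22% of residual variance under equal correlation of 0.6 to 0.9. The saving shrinks as correlation decays with time and is absent in a case such as 0.8/0.8/0.7. A reader might take the 25% reduction as the general result. It applies only to unadjusted change, and only under equal correlation. The hsCRP count of two samples depends on a partly redacted footnote.

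**What to change.** In SAP 6.2.1, define baseline for ELF (score and components) and for hsCRP as the mean of the last two non-missing pre-dose values, taken on the log scale for hsCRP, or the single value where only one exists. Use it as both the reference for change and the model covariate. Keep the last-value baseline as a sensitivity analysis, which also covers the selection and fasting differences at the Baseline visit.

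Fix the rule before outcome data are reviewed. The study is open label, and SAP section 2 provides for results at each interim analysis.

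The cost is one SAP sentence, one derivation change and one extra sensitivity run. No new samples are needed.
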